The use of capsule endoscopy has been approved by the FDA since 2001 for small intestinal bleeding obscure GI Bleeding]. It is very safe, no deaths associated with its use have been reported. More than two million capsule have been used and obstruction and perforation are extremely rare.

Interest in the broader use of VCE is accumulation. In 2004 Sachdev et al reported a pilot study on the use of early use of VCE in acute NHGIB. This showed a 50% reduction to time to diagnosis in 24 patients. More recently studies of VCE deployed in the ED, in patients with upper GI bleeding showed improved management. Our group recently demonstrated that the closer a video capsule is performed to the time of bleeding the higher the likelihood of locating the sources and the higher the therapeutic intervention rate.³ We also have demonstrated that the use of capsule endoscopy in patients with NHGIB has a higher diagnostic yield than does colonoscopy. With improved diagnostic yields, capsule endoscopy may help clinicians by providing guidance in the management of patients with NHGIB.

This protocol is be the first attempt to prospectively examine this concept in a large randomized prospective trial. The questions are, can early capsule intervention decrease time to diagnosis, numbers of procedures and hospital length of stay in patients with non-hematemesis gastrointestinal bleeding.

References:

1. Jawaid S GB, Singh, A, Marshall C, and Cave D. . The epidemiology of gastrointestinal bleeding in an academic emergency department as a basis for

INVESTIGATOR STUDY PLAN - REQUIRED

reconfiguring the conventional approach to its diagnosis and management. .
Gastrointestinal Endoscopy 2013;77:Supplement, Page AB483.

5) Inclusion and Exclusion Criteria*

Inclusion Criteria:

- Age greater than 18 years old
- New onset of melena or hematochezia
- Able to sign consent
- Hemodynamically stable (i.e. blood pressure >100/60 or pulse <110 at the time of consent)

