- ED must plan to admit patient to the hospital or Clinical Decision Unit.

Exclusion criteria:

- Adults unable to consent
- Individuals who are not yet adults (infants, children, teenagers)
- Pregnant women
- Prisoners
- Prior history of gastroparesis
- Prior history of gastric, or small bowel surgery
- Prior history of inflammatory bowel disease
- Concern for infectious colitis
- Non-English speaking
- Evidence of dysphagia at the time of presentation
- Presence of bright red blood per rectum
- Allergy to metoclopramide or erythromycin
- Code status of DNR/DNI or CMO
- Prior history of abdominal radiation
- Presence of ICD or pacemaker or other implanted electronic devices
- Abdominal pain suggesting an acute abdomen or obstruction. In clinical practice, only patients with crampy abdominal pain due to

INVESTIGATOR STUDY PLAN - REQUIRED

Crohn's disease, previous intestinal surgery and a previous history of radiation therapy require a patency capsule or CT enterography before capsule endoscopy.

- Patients who cannot undergo surgery

6) Study-Wide Number of Subjects*

Not applicable – not a multi-site study

7) Study-Wide Recruitment Methods*

Not applicable – not a multi-site study

8) Study Timelines*

1. The participation of individual subjects in this study will be approximately 31-40 days (the length of their hospitalization plus an additional thirty days for follow up).
2. The duration anticipated to enroll all study subjects is about 24 months.
3. The estimated date for the investigators to complete this study and data analysis is two years.

9) Study Endpoints*

The primary endpoint will be time to diagnosis. Secondary endpoints will include hospital length of stay, number of invasive procedures, blood product transfusions.

10) Procedures Involved*

Screening

Patients presenting to the Emergency Room with NHGIB (defined as melena or hematochezia) will be identified by a member of the ED staff.

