Once a subject is identified a page will be sent to a member of the research team (i.e. ED screener, research staff member, GI fellow on call, or GI attending on call) from the ED. In addition to this, the clinical research coordinator and or GI fellow will screen the Emergency Department triage software for patients who are listed as having NHGIB. Based on prior experience Ref Sachdev we expect for every 3 patients asked to participate in the study, there will be 1 patient who agrees to participate. In the emergency department study already cited, the Emergency Department at UMass sees about 350 patients annually for GI bleeding. Of these patients, approximately 230 patients have NHGIB. Given the 3:1 screening ratio, we would expect approximately 75 NHGIB patients every year to agree to participate in the study. In 24 months, we would expect to recruit up to 160 patients to our study.

INVESTIGATOR STUDY PLAN - REQUIRED

Once a subject is identified the subject will then be seen and examined by the GI fellow and attending as per standard of care and asked to participate in the study

Randomization

If inclusion/exclusion criteria are met, the consent discussion takes place and only if the subject agrees and consent is obtained, then the subject is randomized to the “Early Capsule Group” or “Conventional workup Group.” All patients in the “Early Capsule group” will receive the video capsule. Only some of the patients in the “Conventional Workup Group” will receive the capsule as indicated by what is considered the standard workup.

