We will assign patients to study ID numbers consecutively by the order of which they are enrolled in our study. For the Randomization Process we will be utilizing a random sorting generator to assign integers in a random order, corresponding to study IDs which allows researchers to randomly assign study participants into specific study groups. Assignments are put into a mail merge, locked with a password, and printed, then put into a sealed, security envelope, which is sealed with a Study ID sticker. The Randomization Scheme will allow us to attach particular Study ID numbers randomly to particular groups based on our criteria to have 80 subjects in the early capsule group and a comparable number in the conventional workup group. The envelope is only opened once all entry criteria have been met and the subject will be assigned a group. Subjects with a Study ID ending in 1-100 will be enrolled at University Campus. Subjects with a Study ID ending in 101-120 will be enrolled at Memorial Campus. Subjects with a Study ID ending in 121-160 will be enrolled at either campus, depending on enrollment. Enrollment will be competitive at the two locations and there is no specific quota to be reached at either location.

We plan to enroll up to 160 subjects in our study. 80 subjects will be randomized to the “early capsule” deployment group. This means that this group of subjects will have a VCE deployed as soon as possible after presentation to the ED, once the consent process has taken place, eligibility has been confirmed, and the subject has met the standard of care guidelines for preparation before capsule ingestion. Standard preparation for capsule ingestion means that a patient cannot eat for 10 hours prior to deployment of the capsule. Therefore, patients in our study will be asked when they had last eaten. If patients report that they have not eaten anything over the past 10 hours we will deploy the capsule immediately. If, however, patients say that they have eaten something over the past 10 hours we will take note of when they believe they last ate and will deploy the capsule 10 hours after the time that they last ate. In the pilot [Sachdev] study all patients in the early capsule arm received the capsule within a mean of 4 hours of admission to the ED, and none had food in the stomach on capsule examination.

INVESTIGATOR STUDY PLAN - REQUIRED

Procedure

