Initial screening of subjects will be performed in the Emergency Room at the UMass Memorial Medical Center – University Campus-University Campus and UMass Memorial Medical Center – Memorial Campus as discussed in Section 10. Review of video capsule recordings will occur at the GI endoscopy clinic at the same campus.

22) Resources Available

The Principal Investigator is a board certified gastroenterologist with extensive experience at reading video capsules. He will oversee all aspects of the research to ensure it is conducted correctly and that all staff are properly trained on their roles and responsibilities. He will be assisted by sub-investigators who are physicians (attendings, fellows, and/or residents) in the Department of Medicine and Emergency Medicine.

Gastroenterology fellows and Medicine residents will all be used to screen potential candidates for this study once they are notified by the paging process described previously. All fellows and residents will have the appropriate CITI training and will be added to the list of project personnel prior to interacting with or obtaining consent from subjects. They will be responsible for reviewing the inclusion and exclusion criteria with the subject and with obtaining consent for the capsule endoscopy if the subjects agree to take part in the study.

For subjects who agree to take part in the study, Gastroenterology fellows and Medicine residents will also be tasked with administering the capsule

INVESTIGATOR STUDY PLAN - REQUIRED

and with following the results on the RTV as described previously. Fellows and residents performing this task will have the appropriate training and experience in administering the capsule. The Principal Investigator will personally oversee the training of the fellows and residents and personally demonstrate to them how to administer the capsule. The Principal Investigator will be available for any questions that may come up if a fellow or resident has difficulty initiating the capsule. Fellows and residents may also order prokinetic agents such as metoclopramide and erythromycin as described above. The decision to order prokinetics comes after the fellows and residents have discussed using those agents with the Principal Investigator who is a world-renowned authority on capsule endoscopy and the use of prokinetic agents for the purpose of their use.

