PUBLISH DATE JUNE 20, 2018

STATISTICAL ANALYSIS PLAN

TITLE: A comparison of early deployment of a video capsule (Endocapsule EC-10: Olympus Tokyo. Japan) in the Emergency Department versus conventional work-up of non-hematemesis gastrointestinal bleeding [NHGIB].

NCT02442830

[name], PHD, PRINCIPAL INVESTIGATOR

STATISTICAL ANALYSIS PLAN

Study outcomes:

The primary outcome for this study was the rate of localization of bleeding during hospitalization. Localization of bleeding was defined as identification of blood or identification of a lesion with high-risk stigmata of recent hemorrhage (SRH). Secondary outcomes included, overall rate of localization of bleeding by the end of admission, anatomic location of bleeding or the bleeding source, rate of endoscopic therapy, rate of readmission, rate of diagnosis of vascular lesions (defined as Dieulafoy's lesions or angioectasias), rate of re-bleeding within 30 days of discharge, rate of all-cause mortality within 30 days of hospitalization, cumulative direct hospital costs by the end of admission, and overall rate of identifying the etiologic diagnosis.

Sample size calculation:

The study was planned as a superiority trial and the estimated probability of localization of bleeding during hospitalization in the Early Capsule arm to be two times greater than that of the Standard of Care arm (i.e. estimated hazard ratio of 2.00). We found no prior studies similar to our methodology, so prior experience at our institution guided the estimation of effect. Power analysis revealed that for this effect size to be detected (80% chance) as significant at the 5% level, a sample of at least 72 patients (36 per group) would be required.

Statistical analysis:

Patient characteristics were described as means with standard deviation (SD) or as proportions. Time to localization and time to first procedure were described using medians with interquartile range (IQR). Hospital costs were described in US dollars (USD).

Independent variables selected for analysis included those previously suggested as prognostic indices for NHGIB. Variables chosen for analysis included gender, race, age, vital signs at admission, use of anticoagulants, use of non-steroidal anti-inflammatory drugs (e.g. aspirin and ibuprofen; NSAIDs), use of a P2Y₁₂ inhibitor (e.g. clopidogrel), factors that contribute to the Glasgow-Blatchford Score, and type of bleeding at admission (i.e. hematochezia, melena, or symptomatic anemia).

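### The hemodynamic entry criterion joins its two limits with *or*, so a patient who fails one of them still counts as stable

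*Protocol*

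**What the plan says.** The inclusion list in Protocol section 5 contains one hemodynamic requirement: "Hemodynamically stable (i.e. blood pressure >100/60 or pulse <110 at the time of consent".

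The entry criteria lead directly to enrolment. Under Randomization in section 10, "If inclusion/exclusion criteria are met, the consent discussion takes place", and later "The envelope is only opened once all entry criteria have been met and the subject will be assigned a group". Before that, under Screening in the same section, "the subject will then be seen and examined by the GI fellow and attending as per standard of care and asked to participate". Section 22 gives the gastroenterology fellows and medicine residents the eligibility check: "They will be responsible for reviewing the inclusion and exclusion criteria with the subject".

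The SAP does not restate the limits. It uses vital signs only as candidate variables: "Variables chosen for analysis included gender, race, age, vital signs at admission".

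**The concern.** The abbreviation *i.e.* presents the bracket as the meaning of stable, not as an example of it. With *or* between the limits, passing one offsets failing the other. The written rule therefore admits a hypotensive patient whose pulse is below 110, and a patient with a pulse of 110 or more whose pressure is above 100/60. Neither fits the label on the criterion.

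What is at stake is patient safety at entry. Under section 10 the capsule is given only once 10 hours have passed since the last meal, real-time checks may run to eight hours after ingestion, and the reading is ideally reported 1–4 hours after recording stops. For a patient who has just eaten, that sequence could take up to 10 + 8 + 4 = 22 hours, although the real-time checks can show blood sooner and nothing in the protocol forbids urgent care. No hemodynamic rule for leaving the sequence is given. Section 15 says no risks are anticipated from early deployment. That is easier to support if only stable patients enter.

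**Working it through.** **What the written rule does.** Let A be blood pressure above 100/60, read as systolic above 100 and diastolic above 60 (the protocol does not spell this out). Let B be pulse below 110.

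- As written, a patient is eligible if A or B holds, and so is refused only if both fail.
- With *and*, a patient is eligible only if A and B both hold, and so is refused if either fails.

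The vital signs below are illustrative and do not come from the documents.

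| Blood pressure, pulse | A | B | Written rule (*or*) | With *and* |
|---|---|---|---|---|
| 105/65, 105 | met | met | in | in |
| 105/65, 140 | met | failed | in | out |
| 80/40, 105 | failed | met | in | out |
| 80/40, 115 | failed | failed | out | out |
| 130/58, 72 | failed | met | in | out |

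The two rules differ exactly for patients who fail one limit and meet the other.

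**Whether other text closes the gap.**

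- *Exclusion criteria (section 5).* None names hypotension, tachycardia, shock or instability. The nearest, "Presence of bright red blood per rectum", concerns the type of bleeding, not vital signs.
- *Randomization (section 10).* It requires only that the entry criteria be met and adds no further hemodynamic check.
- *Withdrawal (section 14).* The reasons are inability to swallow the capsule, a source outside the stomach or intestines, and the subject's own request.
- *SAP.* Admission vital signs are analysis variables, and no entry limit is repeated or corrected.

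Nothing turns the *or* into an *and*.

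**What the correction would cost in recruitment.** No sample size, power or alpha figure in the plan depends on this criterion, so there is no stated figure to reproduce. Section 10 expects about 75 participants a year, or 75 × 2 = 150 in 24 months. The share who fail exactly one limit is not given. Over an assumed range:

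| Assumed share lost | Remaining of 150 |
|---|---|
| 0% | 150 |
| 5% | 142.5 |
| 10% | 135 |
| 20% | 120 |

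The SAP's minimum is 72. Recruitment would fall to that level only with a loss of (150 − 72)/150 = 52%.

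The SAP's figure rests on a different primary outcome from the protocol's, so I also checked the protocol's own inputs: means of 30 and 15.9 hours, with SDs of 6.1 and 12.2.

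- Pooled SD = √((6.1² + 12.2²)/2) = 9.645.
- d = (30 − 15.9)/9.645 = 14.1/9.645 = 1.46. The protocol prints 1.49301; the difference does not matter here.
- With 60 per group (120 in total), the noncentrality is 1.46 × √(60/2) = 8.0, far above the two-sided 5% critical value of about 2, so t-test power is above 99%.

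**The case against.** The strongest reply is that the requirement is stability itself and the bracket is loose drafting. Section 10 does use *i.e.* loosely: under Review and Follow-Up it introduces the same list of procedures once with *e.g.* and once with *i.e.* A clinician would not call 80/40 stable. The GI fellow and attending also examine each patient before asking for participation, the patient must be able to consent, the ED must already plan admission, and capsule findings lead only to a recommendation. These points stand and lower the practical risk. None of them attaches a threshold, so someone applying the written numbers could still properly enrol such a patient.

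A second objection is that the remedy is not free. With *and*, a patient at 130/58 with pulse 72 is refused because of the diastolic limit alone, although few would call that patient unstable. This is a fair point. It is a reason to confirm that the diastolic limit is intended, not a reason to keep *or*.

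A third is that 120 participants would be 25% below the planned maximum of 160. That is correct as arithmetic ((160 − 120)/160 = 25%). But 160 is an upper limit, the protocol's own annual rate already gives only 150, and the 20% loss is the top of an assumed range.

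Finally, no harm or bias is quantified. That is true. The number of affected patients cannot be derived from the documents.

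**Conclusion.** The concern holds. As written, the criterion admits anyone who meets one of its two limits, which contradicts its label, and no other text in the protocol or SAP corrects it. It is an eligibility and safety defect. It does not threaten the validity of the comparison, because the rule applies before randomization and identically to both arms. The conclusion rests on the literal wording; *and* may have been intended, and may have been applied in practice, but the documents do not say so. The number of patients affected is unknown. Under an assumed loss of 0–20%, correcting the rule leaves 120–150 of about 150 expected participants, which is enough under both the SAP's minimum and the protocol's own power inputs.

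**What to change.** Amend the criterion in section 5, and any eligibility checklist, to require blood pressure above 100/60 **and** pulse below 110 at the time of consent. While doing so, confirm whether the diastolic limit is intended; if only systolic pressure matters, say so. Record both values at consent, since the hospitalization data listed in section 10 do not name blood pressure or pulse.

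The cost is a one-word amendment, matching checklist wording and some loss of eligible patients.

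The SAP is written in the past tense, so enrolment may be complete. In that case the sponsor should state which rule was applied and, where consent-time values exist, report by arm how many participants met only one limit.

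### The protocol gives two study-ID rules that cannot both be followed at two campuses; balance is assured only at 80:80 over all 160 IDs, and campus is not in the planned analysis

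*Protocol*

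**What the plan says.** Protocol Section 10 (Randomization) sets out the allocation in one paragraph.

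- **Order of IDs:** "We will assign patients to study ID numbers consecutively by the order of which they are enrolled in our study".
- **List:** the arms come from "utilizing a random sorting generator to assign integers in a random order, corresponding to study IDs". The only stated constraint is 80 in the early capsule arm and a similar number in the other. No block size or stratum is given.
- **Envelopes:** each assignment is sealed in an envelope labelled with its Study ID and opened only after eligibility is confirmed.
- **Campus ranges:** 1-100 are set aside for University and 101-120 for Memorial. The remaining 40 IDs form a common pool: "Subjects with a Study ID ending in 121-160 will be enrolled at either campus, depending on enrollment".
- **Quota:** on targets per campus, the paragraph ends with "Enrollment will be competitive at the two locations and there is no specific quota to be reached at either location".

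Protocol Section 21 has screening in two emergency departments, with recordings reviewed at the endoscopy clinic of the same campus.

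The SAP (Sample size calculation) states that "a sample of at least 72 patients (36 per group) would be required". Its Statistical analysis section plans a Kaplan-Meier comparison with a log-rank test and mentions no stratification. Of the variables for adjustment it says "Variables chosen for analysis included gender, race, age, vital signs at admission, use of anticoagulants", and the list goes on to other drugs, components of a bleeding score and type of bleeding. Campus is not named.

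**The concern.** A patient's ID determines the envelope, and the envelope determines the arm. Two incompatible ID rules therefore leave the allocation procedure undefined. Nobody could later confirm from the protocol that each patient received the next envelope due. The shared range 121-160 adds to this: the text does not say who holds those envelopes, how the next number is claimed across campuses, or when a campus may start drawing on them.

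Separately, an unrestricted sort fixes the arm totals only at the end of the list. If enrolment ends early, or if one looks within a campus, the arms may be uneven. Should the campuses differ in how fast a bleeding source is found, an uneven split would carry some of that difference into the treatment comparison, and neither the planned test nor the named covariates account for campus.

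**Working it through.** **1. The two ID rules side by side.** Under strict consecutive numbering, the first 100 enrolled take IDs 1-100, all reserved for University. Memorial's first ID is 101, so Memorial could enrol nobody until 100 University patients were in, and nobody by 72. If instead each campus works through its own range, IDs no longer follow the order of enrolment once both campuses are recruiting. The ranges also fit poorly with having no quota: using all 160 IDs requires 100 to 100 + 40 = 140 patients from University and 20 to 20 + 40 = 60 from Memorial.

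**2. The SAP's own figure.** Inputs: hazard ratio 2.00, 80% power, 5% level (two-sided assumed). Freedman's formula gives (1.960 + 0.842)² × [(1 + 2)/(1 − 2)]² = 7.85 × 9 = 70.6, so 71 events, or 72 in equal arms. This reproduces the stated 72, as a count of events; it equals patients only if every patient has the event.

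**3. Chance imbalance.** For a random sort of 80 + 80, the number X of early-capsule assignments among any n IDs is hypergeometric, P(X = x) = C(80, x)·C(80, n − x)/C(160, n), provided the choice of IDs does not depend on envelope contents.

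| IDs considered | SD of X | Exactly equal | 95% range | Uneven splits |
|---|---|---|---|---|
| Memorial, 20 | 2.10 | 19% | 6-14 | 13:7 or worse 23%; 14:6 or worse 9% |
| University, 100 | 3.07 | 13% | 44-56 | 55:45 or worse 14%; 60:40 or worse 0.2% |
| Any 72 | 3.16 | 13% | 30-42 | 40:32 or worse 27%; 42:30 or worse 8% |

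If 12 of the 72 came from Memorial (assumption), 9:3 or worse among them has probability 13%. In simulation, reaching 36 in both arms takes a median of 76 enrolments (95% range 72-86).

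**4. Cost in power.** Schoenfeld's approximation with D = 72 events, hazard ratio 2.00 and fraction p in one arm: power = Φ(√[D·p(1 − p)]·ln 2 − 1.960).

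- 36:36: √18.00 × 0.693 − 1.960 = 0.981, power 83.7%
- 40:32: √17.78 × 0.693 − 1.960 = 0.963, power 83.2%
- 42:30: √17.50 × 0.693 − 1.960 = 0.940, power 82.6%

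**5. Possible size of a campus effect.** The documents give no campus difference, so gaps of 3-12 hours in time to diagnosis are assumed. The standard deviations (6.1 and 12.2 h) and the planned difference (30 − 15.9 = 14.1 h) are from Protocol Section 12.

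- Full trial, 80 per arm, Memorial split 13:7 with no other Memorial patients: campus mix differs by 6/80 = 7.5 points. Shift 0.075 × 3 to 0.075 × 12 = 0.2 to 0.9 h. Standard error √[(6.1² + 12.2²)/80] = 1.5 h.
- 36 per arm, Memorial split 9:3: mix differs by 6/36 = 16.7 points. Shift 0.5 to 2.0 h. Standard error √[(6.1² + 12.2²)/36] = 2.3 h.

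Both shifts stay below one standard error, although these splits are themselves unlikely.

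**6. What blocking would give.** An incomplete block leaves a difference of at most half its size. With blocks no larger than 4 (assumption), that is 2 per campus and 4 overall, so no worse than 38:34 at 72. With a largest block of 6 (assumption), it is 3 per campus and 6 overall, so no worse than 39:33.

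**The case against.** The strongest reply is that a random sort followed in order is a valid randomisation. Chance imbalance is part of the sampling error that the test already allows for, and the power cost is about one point. That stands. Four further points limit the concern.

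- A reader might infer that the arms are unbalanced. The documents show only that balance is not guaranteed; even the absence of blocks is inferred from the described sort and from silence.
- A reader might infer that the shared pool lets staff choose a patient's arm. The envelopes are sealed and opened only after eligibility is settled, and nothing in the text gives a route to knowing their contents. What is missing is a fixed, auditable order of use.
- A reader might infer that endoscopy access or gastroenterology teams differ by campus. Section 21 supports reading by campus and no more. Section 10 has the principal investigator or a sub-investigator read the recordings, and the protocol calls itself single-site.
- The figure of 72 is a minimum. The protocol plans up to 160, and neither document says that enrolment stops near 72.

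The SAP also adds covariates found to be uneven between the arms, and its list of variables may not be exhaustive, so the route to adjusting for campus is not clearly closed. But campus is not named, and whether it would be considered is left to judgement.

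Blocking has its own cost. Staff see each arm once it is assigned, so small fixed blocks make later assignments deducible. This argues for varying block sizes and against blocks of 2.

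**Conclusion.** The contradiction in the ID rule is plain on the page and needs correcting, because that rule determines the arm. Balance is assured only at 80:80 over the full list. Within Memorial's reserved range, or near the SAP's minimum, moderate imbalance is fairly likely (13:7 or worse 23%; 40:32 or worse 27%). The imbalance follows from having no blocks or strata, not from the numbering conflict.

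This is a matter of documentation and precision. It does not bias the comparison, and the power cost at 72 is about one point, on the assumption of 72 events and a hazard ratio of 2.00. Confounding by campus is possible but cannot be sized from the documents; under the assumed gaps it stays below one standard error. The imbalance figures assume a single unrestricted sort of 80 and 80, and those at 72 matter only if enrolment ends near that number.

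**What to change.** - **ID rule:** state one rule, with IDs consecutive within campus, a separate ID series and envelope set for each campus, and no shared pool. Replace 121-160 with extra envelopes on each campus list.
- **Envelopes not yet used:** generate each campus list in permuted blocks of randomly varying size, avoiding blocks of 2, and keep the sizes from recruiting staff. The cost is reprinting, plus some predictability because the arms are visible.
- **Analysis:** stratify the log-rank test by campus and include campus in the adjusted model whatever its univariate p-value. This takes one or two lines in the SAP and no extra patients.
- **If enrolment is complete**, as the past tense of the 2018 SAP suggests: document how IDs and envelopes were actually issued, including 121-160; state whether any blocking was used; report arm by campus; and give the campus-stratified result as a sensitivity analysis. The cost is a short record and one table, if campus was recorded.
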